10.0 ADVERSE EVENTS

10.1 Definitions

10.1.1 Adverse events

An adverse event is defined as any untoward medical occurrence in a patient or a study subject receiving a pharmaceutical product (including the study drug). It does not necessarily have an apparent causal relationship with this pharmaceutical product (including study drug).

An adverse event can therefore be any unfavorable and unintended sign (e.g., a clinically significant laboratory abnormality), symptom, or disease temporally associated with the use of a pharmaceutical product (including the study drug), regardless of whether it is considered related to the pharmaceutical product (including the study drug) or not.

10.1.2 Considerations for adverse events

Generally unfavorable findings are described below:

- Newly diagnosed disease or unexpected aggravation of existing symptom (intermittent event of an existing symptom is not considered an adverse event)
- Requiring action or medical practice
- Requiring invasive diagnostic treatment
- Requiring discontinuation or a change in the dose of the study drug or a concomitant medication
- Considered unfavorable by the principal investigator or the investigator

Diagnosis name and signs/symptoms:

Adverse events shall be recorded by diagnosis name. Accompanying signs (including abnormal laboratory values) and symptoms shall not be recorded as adverse events. If an adverse event could not be expressed by a diagnosis name, the signs or symptoms shall be recorded as the adverse event.

Laboratory test values:

Abnormal laboratory values shall be recorded as adverse events when the principal investigator or the investigator judges the results are clinically problematic (in other words, when certain action or medical practice is required, or when the principal investigator or the investigator judges the change has exceeded the normal physiological variation range of the study subject). Retest and/or continued monitoring of an abnormality are not considered medical practice. Also, repeated or additional

conduction of non-invasive tests for verification, evaluation, and monitoring of an abnormality are not considered medical practice.

However, when abnormal laboratory values are the accompanying symptoms of a disease diagnosed as an adverse event (e.g., increased creatinine due to renal dysfunction, etc.), the adverse event shall be handled by its diagnosis name.

Pre-existing conditions (a disease or symptom that is present at the start of the screening period or that is observed from the start of the screening period until before the start of study drug administration):

A disease or symptom that is present at the start of the screening period or that is observed from the start of the screening period until before the start of study drug administration are considered a concurrent disease and not considered an adverse event. When a concurrent disease is aggravated, the aggravation shall be determined as an adverse event and the principal investigator or the investigator shall record on the CRF that the adverse event is an aggravation of the concurrent disease (e.g., “aggravation of hypertension,” etc.).

If a study subject has a pre-existing episodic condition (e.g., asthma, epilepsy), each episode shall be recorded as an adverse event if the episodes become more frequent, serious, or severe in nature. If a study subject has a chronic concurrent condition (e.g., cataracts, rheumatoid arthritis), worsening of the condition shall be recorded as adverse event if the degree of the worsening exceeds that which would be expected. The principal investigator or the investigator shall ensure that the adverse event term to be reported represents the change in the condition from baseline (e.g. “worsening of...”).

Worsening of adverse events:

If a study subject experiences a worsening of the adverse event after a change of the study drug, or secondary signs and symptoms are caused by the adverse event, the worsening or the secondary signs and symptoms shall be recorded as a new adverse event on the CRF. The principal investigator or the investigator shall use an adverse event term that explicitly means a change of the condition (e.g., “worsening of...”).

Change of severity of adverse events:

If the study subject experiences changes in the severity of an adverse event, the event shall be recorded once, at its peak severity.

Previously planned surgery or treatment:

Preplanned surgeries or treatment that were scheduled before the start of study drug administration shall not be considered adverse events. However, when the existing symptom is aggravated to a degree requiring emergency surgery or treatment, the condition or the event shall be considered an

adverse event. A concurrent disease that resulted from previously planned surgery shall be reported as an adverse event.

Non-urgent surgery or treatment:

Non-urgent surgery or treatment that does not induce a change in the condition of a study subject (cosmetic surgery, etc.) shall not be considered an adverse event; However, it shall be recorded in the source documents. Concurrent diseases due to a non-urgent surgery shall be reported as an adverse event.

The Insufficient clinical response (lack of efficacy):

Insufficient clinical response, efficacy, or pharmacological action shall not be recorded as an adverse event. The principal investigator or the investigator shall make the distinction between worsening of a pre-existing condition and lack of therapeutic efficacy.

Overdose:

Overdose of any medication without manifested symptoms shall not be recorded as an adverse event, but the overdose shall be recorded on the “Overdose” page of the CRF. Any manifested symptoms shall also be recorded as adverse events on the “Adverse events” of the CRF.

10.1.3 Serious adverse event

Of all the unfavorable medical events that develop with administration of a pharmaceutical product (including study drug) (irrespective of dose), a serious adverse event is an event that:

1. results in death,
2. is life threatening*,
3. requires inpatient hospitalization or prolongation of existing hospitalization,
4. results in persistent or significant disability/incapacity,
5. leads to a congenital anomaly/birth defect, or
6. other medically significant condition: a medically important event that causes a risk to a study subject even if it is not immediately life-threatening and does not result in death or hospitalization, or requires an action or treatment to prevent the results described in 1 to 5 above. In addition, points described in the Takeda Medically Significant Adverse Event List (Table 10 (a)) are included in this section.

* The term “life threatening” refers to an event in which the study subject was at risk of death at the time of the event; it does not refer to an event that hypothetically might have caused death if it was more severe.

Table 10.a Takeda Medically Significant AE List

Acute respiratory failure/acute respiratory distress syndrome (ARDS)	Hepatic necrosis
Torsades de pointes/ ventricular fibrillation/ventricular tachycardia	Acute hepatic failure
Malignant hypertension	Anaphylactic shock
Convulsive seizure (including convulsion and epilepsy)	Acute renal failure
Agranulocytosis	Pulmonary hypertension
Aplastic anemia	Pulmonary fibrosis (including interstitial pneumonia)
Toxic epidermal necrolysis/ Oculomucocutaneous syndrome (Stevens-Johnson syndrome)	Neuroleptic malignant syndrome/ malignant hyperpyrexia
	Spontaneous abortion/ stillbirth and fetal death
	Confirmed or suspected transmission of infection by a medicinal product
	Confirmed or suspected endotoxin shock

10.1.4 Severity of adverse events

The severity of adverse events shall be classified and defined as shown below.

Mild	The event is transient and easily tolerated by the subject.
Moderate	The event interrupts the subject's usual activities.
Severe	The event causes considerable interference with the subject's usual activities.

10.1.5 Causality of adverse events

The causal relationship of each adverse event to the study drug shall be classified and defined as shown below.

Related	An adverse event that follows a temporal sequence (including clinical course after discontinuation), or an adverse event in which there is at least a reasonable probability that a causal relationship to the study drug cannot be ruled out, although other factors such as underlying disease, concurrent diseases, or concomitant drugs/treatment are also suspected.
Not related	An adverse event that does not follow a temporal sequence from administration of the study drug. Very likely due to other factors such as underlying disease, concurrent diseases, or concomitant drugs/treatment.

10.1.6 Relationship to study procedures

The relationship shall be recorded as “Yes” if the principal investigator or the investigator considers that there is reasonable possibility that an adverse event is due to a study procedure. Otherwise, the relationship shall be recorded as “No.”

10.1.7 Date of onset

The date of onset of adverse event shall be determined according to the following rules:

Adverse events	Date of onset
Signs, symptoms, diseases (diagnoses)	The date on which the first signs/symptoms were noted by the study subject and/or the principal investigator or investigator.
Asymptomatic diseases	The date on which a diagnosis was confirmed through a test(s). The date on which a diagnosis was confirmed, even when the test results indicate an old sign(s) of the disease or an approximate time of its onset.
Exacerbation of concurrent diseases	The date on which the first worsening of diseases/symptoms was noted by the study subject and/or the principal investigator or investigator.
Onset of a test abnormality after the start of study drug administration	The date on which a clinically significant laboratory abnormality was detected.
Worsening of a baseline test abnormality after initiation of study treatment	The date on which a clear increase/decrease in a laboratory parameter was clinically confirmed based on the time profile of the parameter.

10.1.8 Date of resolution

The date of resolution of an adverse event is the date on which the study subject recovered (including resolution with sequelae). If a study subject died due to the adverse event concerned, it shall be the date of death. The adverse event shall be recorded as “ongoing” if the study subject has not yet recovered by the end of the study.

10.1.9 Actions taken for the study drug

Actions taken for the study drug shall be classified or defined as shown below.

Drug withdrawn	The study drug is discontinued because of an adverse event (including withdrawal by the study subject at his/her own discretion). When the study is discontinued but study drug administration is still continued, the classification should be “Dose not changed.”
----------------	--

Dose not changed	
The dose was not changed after the onset of the adverse event.
 
The study drug was discontinued, reduced, or increased because of another adverse event.
 
The study drug was discontinued or reduced for a reason other than the adverse event, e.g., inadvertence of the study subject.

Unknown	It has not been possible to determine what action has been taken because the study subject is lost to follow-up.
Not Applicable	The administration of the study drug had already been completed or discontinued before the onset of the adverse event.
Dose reduced	The dose of the study drug is reduced because of an adverse event (including dose reduction by the study subject at his/her own discretion).

10.1.10 Outcome

Outcome of adverse events is classified as follows:

Category	Criteria
Recovered	
 - Disappearance or recovery of symptoms and findings - Laboratory values returned to normal or baseline
Improved	
 - The intensity is lowered by one or more stages - Symptoms or findings mostly disappeared - Laboratory values improved, but have not returned to normal or baseline - The study subject died from a cause other than the concerned adverse event while the condition was resolving (recording of the date of death unnecessary)
Not recovered	
 - No change in symptoms, findings, or laboratory data - The symptoms, findings, or laboratory data on the final day of observable period were aggravated compared with the date of onset - Irreversible congenital anomaly - The study subject died from another cause before resolution of the concerned adverse event (recording of the date of death unnecessary)
Recovered with sequelae	
 - Disability that disturbs daily life
Death	
 - Direct relationship between death and the concerned adverse event, etc. “Direct relationship” means that the concerned adverse event, etc. was the cause of death, or the concerned adverse event, etc. was clearly responsible for death. - Outcome of an adverse event which was not determined (judged, presumed) a direct cause of death observed in the same study subject is not considered as death. - The date of death shall be recorded.
Unknown	
 - Follow-up specified in the protocol after the date of onset was not possible due to change of hospitals or relocation, etc.

10.2 Procedures

10.2.1 Collection and reporting of adverse events

10.2.1.1 Adverse event collection period

Adverse events shall be collected from the start of administration with the study drug until completion of the treatment period (or discontinuation).

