6.0 CLINICAL STUDY DESIGN

6.1 Clinical study design

<Clinical study design>

This is an multicenter, randomized, open-label study to explore the effects of omega-3-acid ethyl esters on the lipid and lipoprotein profile in the blood in hyperlipidemic patients receiving a HMG-CoA reductase inhibitor in comparison with the control group of patients not treated with omega-3-acid ethyl esters in an unblinded manner by use of HPLC using highly-sensitive gel filtration columns, which is a technique for analyzing lipoprotein.

Considering the factors potentially biasing the lipid and lipoprotein profile in the blood between the treatment groups, study subjects who gave consent and were assessed as eligible in the eligibility assessment will be stratified for allocation by the factors of “fasting TG (< 300 mg/dL or \geq 300 mg/dL) and age (< 65 years or \geq 65 years) at the start of the screening period” (1:1 ratio).

<Treatment>

[1] Study drug

Omega-3-acid ethyl esters

[2] Dosage regimen

The group treated with omega-3-acid ethyl esters: Hyperlipidemic patients receiving a HMG-CoA reductase inhibitor* will orally receive omega-3-acid ethyl esters 2 g immediately after meal twice daily.

The group not treated with omega-3-acid ethyl esters: Hyperlipidemic patients receiving a HMG-CoA reductase inhibitor* will continue to receive the HMG-CoA reductase inhibitor at the same dose regimen as at the time of informed consent.

*: Irrespective of the treatment groups, patients will receive a HMG-CoA reductase inhibitor at a consistent dose regimen that should have been stable for \geq 4 weeks prior to informed consent. Change of the HMG-CoA reductase inhibitor and its dose regimen is not allowed throughout the screening period and the treatment period.

[3] Duration of treatment

8 weeks

<Planned number of study subjects>

50 patients evaluable for the primary endpoint

(25 patients in the group treated with omega-3-acid ethyl esters, 25 patients in the group not treated with omega-3-acid ethyl esters)

<Number of study sites>

Around 5 sites

<Duration of treatment and number of visits for a study subject>

[1] Duration of treatment

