8.0 STUDY TREATMENT

8.1 Study drug

Generic name: Omega-3-acid ethyl esters

Chemical name: Ethyl icosapentate;

ethyl(5Z,8Z,11Z,14Z,17Z)-icosa-5,8,11,14,17-pentaenoate

Docosahexaenoic acid ethyl ester;

ethyl(4Z,7Z,10Z,13Z,16Z,19Z)-docosa-4,7,10,13,16,19-hexaenoate

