9.1.7 Concurrent disease

A concurrent disease shall be defined as a disease or symptom present at the start of the screening period or observed from the start of the screening period until before the start of study drug administration. Clinically problematic laboratory test data, ECG findings, and abnormal physical examination findings observed at the start of the screening period shall be considered as a concurrent disease at the discretion of the principal investigator or investigator. The content of concurrent disease (diagnosis) shall be investigated.

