9.3.4 Completion (Visit 4) or discontinuation

Visit 4 is the last visit, and the principal investigator or the investigator shall perform the following tests, observations, and evaluations for each study subject. If the study drug administration is discontinued, study subjects should, to the extent possible, undergo tests within 3 days from the last dose taken.

Items to be checked: Food and drink consumption before visit

- Confirm that alcohol was not consumed from 9:00 pm 2 days before the visit and food was not consumed from 9:00 pm the day before the visit
 - Confirm that excessive eating/drinking and extreme change in dietary content were not made on the day before the visit.
-
- Physical examination
 - Vital signs
 - Concomitant drugs
 - Laboratory tests
 - Treatment compliance
 - Evaluation of adverse events

At completion of the clinical study, the status of all study subjects administered the study drug shall be recorded on the CRF.

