5 OTHER DATA HANDLING

[Data Handling for Study Drug]

- Duration of Treatment(Treated with Omega-3 FAE)

Duration of Treatment = Date of the Last Dose – Date of the First Dose + 1

[Data Handling for Duration of Hyperlipidemia]

- Duration of hyperlipidemia (year)

Duration of hyperlipidemia (year) = (Date of first dose (year/month) – Onset/Diagnosis

Date of hyperlipidemia (year/month)) / 12 (rounded off to two decimal places)

If only the month of the onset of hyperlipidemia is unknown, the month of the onset of hyperlipidemia is regarded as “January”.

[Data Handling for Below (or Above) the limit of Quantification]

- Efficacy Data

(Laboratory Test (except Total Cholesterol, TG, HDL-C) and Lipoprotein Fraction)

Below (or equal to) the limit of Quantification: Lower Limit of Quantification to be replaced.

Above (or equal to) the limit of Quantification: Upper Limit of Quantification to be replaced.

- Safety Data

(Vital Sign and Laboratory Test (Total Cholesterol, TG, HDL-C))

Below (or equal to) the limit of Quantification: 0 to be replaced.

Above (or equal to) the limit of Quantification: Upper Limit of Quantification to be replaced.

[Data Handling for Adverse Event]

- An adverse event is defined as any untoward medical occurrence in a patient or a subject receiving a pharmaceutical product (including the study drug). It does not necessarily have an apparent causal relationship with this pharmaceutical product (including study drug). A treatment-emergent AE (TEAE) is defined as an AE which occurs after taking the first dose of trial medication.
The first dose date of “Not treated with Omega-3 FAE” is defined as the next day of the visit in Week 0.
- Time to first Onset
Time to first Onset=AE Start date - The first dose date + 1
- Related AE
AE is classified into Related/Not Related only for Treated with Omega-3 FAE group
- Non-Serious TEAEs
Non-Serious TEAE is defined as Non-Serious TEAEs of at least 5% in any treatment group by SOC and PT.

[Laboratory Test]

- (EPA+DHA)/AA Ratio
(Eicosapentaenoic Acid + Docosahexaenoic Acid)/ Arachidonic Acid
- DHA/AA Ratio
Docosahexaenoic Acid / Arachidonic Acid
- non-HDL
Total Cholesterol - HDL-C

6 SUBJECTS, DEMOGRAPHIC and OTHER BASELINE CHARACTERISTICS

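### The protocol starts adverse-event collection at study drug administration, which controls never receive; this conflicts with the visit schedule and the SAP and risks under-recording of control events

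*Protocol*

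**What the plan says.** **Rules tied to study drug (Protocol)**

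- 10.2.1.1: "Adverse events shall be collected from the start of administration with the study drug until completion of the treatment period (or discontinuation".
- 10.2.2 applies the serious-event procedure to events arising within that collection period.
- 9.1.7 counts as concurrent disease anything present at screening or "observed from the start of the screening period until before the start of study drug administration". 10.1.2 adds that such conditions "are considered a concurrent disease and not considered an adverse event", although a later aggravation of one is an adverse event.
- 9.3.4: at completion, "the status of all study subjects administered the study drug shall be recorded on the CRF".
- 8.1 identifies the study drug: "Generic name: Omega-3-acid ethyl esters". Under 6.1, controls "will continue to receive the HMG-CoA reductase inhibitor at the same dose regimen as at the time of informed consent". There is no placebo.

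**Text covering both arms**

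- Protocol 9.3.3 and 9.3.4 list adverse-event evaluation at Visits 3 and 4 for every subject. 10.2.1.2 requires a symptom check at each visit and entry of all adverse events in the CRF. Appendix A has a single adverse-event row that is not limited to one arm.
- Protocol 13.1.4 tabulates adverse events by treatment group.
- SAP section 5 says the control first-dose date "is defined as the next day of the visit in Week 0" and limits the related/not related classification to the treated group. SAP section 2 uses the same control Day 1.

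**The concern.** The sentence that tells sites when to begin collecting adverse events names an event that never happens in one of the two arms. The companion rule on concurrent disease ends its window at that same event. A site that follows these sentences has a textual reason to enter a new control illness as concurrent disease, or not to enter it at all. Through 10.2.2, the same reasoning would place a control's serious event outside the reporting procedure.

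The SAP's notional first-dose date does not remove the problem. It sorts events already recorded as adverse events. It is not an instruction to sites and cannot recover an event that was never entered.

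Two things are at stake: a by-arm table that may overstate harm from omega-3, and complete serious-event reporting for controls. The trial is open-label at around five sites, so staff know each patient's arm and sites may settle the conflict differently. Any shortfall would fall on the control side.

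**Working it through.** The documents contain no adverse-event rate and no calculation to reproduce. Protocol 13.3 sets 25 per arm on feasibility. The main check is therefore a comparison of the texts.

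**Step 1. When does a control's collection period open?**

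| Source | Start or scope | Applies to a control? |
|---|---|---|
| Protocol 10.2.1.1 | Start of study drug | No date exists |
| Protocol 10.2.2 | Within the collection period | No period exists |
| Protocol 9.1.7, 10.1.2 | Concurrent disease until study drug starts | Window never closes |
| Protocol 9.3.3, 9.3.4, 10.2.1.2 | Adverse events evaluated at visits, every subject | Yes |
| Protocol Appendix A | Adverse events followed from Week 0; concurrent disease at Visits 1 and 2 only | Yes |
| SAP 2 and 5 | Day 1 is the day after the Week 0 visit | Yes, for analysis |

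The first three rows give a control no start date. The last three assume there is one. No protocol text reconciles them.

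**Step 2. Is this an isolated slip?** Other safety text is also written for the treated arm. The action codes in 10.1.9 have no entry for a drug never given: the not-applicable code covers only drug already completed or stopped. Section 10.2.1.2 asks for drug causality for every event, whereas SAP section 5 restricts it to the treated group.

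**Step 3. Illustrative size.** Assumptions, none from the documents: the same true proportion p of patients with an event in each arm, and a fraction m of control patients' events not recorded. With n = 25 per arm:

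- expected treated count = 25p
- expected control count = 25p(1 − m)
- spurious gap = p − p(1 − m) = mp

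As a gauge only, I give the exact binomial chance that a two-sided Fisher test would fall below 0.05. The plan makes no such test.

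| p | Expected treated | m = 1: gap, chance | m = 0.5: gap, chance | m = 0: gap, chance |
|---|---|---|---|---|
| 10% | 2.5 | 10 points, 3.3% | 5 points, 1.3% | 0, 0.9% |
| 20% | 5 | 20 points, 38.3% | 10 points, 8.6% | 0, 2.2% |
| 30% | 7.5 | 30 points, 80.7% | 15 points, 15.0% | 0, 2.3% |
| 40% | 10 | 40 points, 97.1% | 20 points, 23.1% | 0, 3.0% |

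For single tables with no control events, the two-sided p-value is 2·C(25,a)/C(50,a). For a = 5 this is 2 × 53,130 / 2,118,760 = 0.0501. For a = 10 it is 2 × 3,268,760 / 10,272,278,170 = 0.0006.

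The m = 1 column is a ceiling: it needs every site to disregard the schedule rows in Step 1. The m = 0 column is what a common understanding of the control start date would give.

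**The case against.** The best defence is that the plan as a whole clearly intends to collect control events. The visit lists and Appendix A cover every subject. After Visit 2 the scheduled item is adverse-event evaluation, not concurrent disease. Protocol 10.1.1 defines an adverse event for a patient on any pharmaceutical product, which includes a statin. The by-group tables would be pointless without control events, as would the SAP's limit on causality. The SAP revision history does not list the control date among the Version 2 changes, so it does not look like a late repair.

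This largely succeeds against a stronger reading that a reader might infer: that control events are concurrent disease under the protocol and the comparison is therefore biased. The documents do not support that. They contain competing instructions, and how sites resolved them is not known. Aggravation of a concurrent disease also remains an adverse event even on the literal reading.

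The defence is also right about a table of 5/25 or 10/25 against 0/25. The Safety Analysis Set in both documents requires a dose of study drug, so a consistently literal reading leaves no control denominator at all. Such a table reads the numerator literally and the denominator by intent.

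What the defence does not remove is the defect in 10.2.1.1, 9.1.7 and 10.1.2. The schedule says when to ask; these sections say what counts and from when. For controls the two disagree.

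The sentence in 9.3.4 matters less. Protocol 12.1 requires a CRF, including completion status, for each consented subject, and SAP 6.1.3.1 reports end-of-study status for all randomised subjects.

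**Conclusion.** The point holds as an internal inconsistency that carries a risk. Read literally, the protocol gives controls no start for adverse-event collection or serious-event reporting and no end to the concurrent-disease window. This contradicts its own schedule, its by-group tables and the SAP's control Day 1. If some sites follow the literal text, control events will be under-recorded and the by-arm table will overstate harm from the drug.

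The size cannot be stated beyond illustration. Under the assumed equal rates of 10% to 40%, the spurious gap is 5 to 20 points if half of control events are missed, and 0 if none are. The 10 to 40 points with all missed is an extreme, not an expectation. All of this rests on assumed event rates and assumed site behaviour. The correction is worth making because it is nearly free and missed events cannot be restored at analysis.

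**What to change.** - In Protocol 10.2.1.1, 10.1.2 and 9.1.7, add that for the group not treated with omega-3 the start is the day after the Week 0 visit, which is the SAP's control Day 1.
- Keep the first-dose date as the start for the treated group. Moving both arms to the day after Visit 2 would create a new mismatch: the Week 0 window runs from Day -15 to Day -1, so a treated patient who started later than the next day would have pre-dose events collected as adverse events, against the SAP's treatment-emergent definition.
- State that 10.2.2 applies to both arms over the period so defined.
- In 9.3.4, record final status for all randomised subjects, in line with SAP 6.1.3.1.

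The Safety Analysis Set wording (Protocol 13.1.1, SAP section 3) is a related gap best corrected at the same time, but a corrected denominator does not supply uncollected events.

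The cost is a few lines of protocol text and slightly more data entry for controls. No visit, test or planned analysis changes.
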